### 9.5. Laboratory Evaluations

Laboratory tests will include chemistry panel, hematology panel, and urinalysis testing. Laboratory tests will be performed at the following time points: at the screening visit, and at week 8. If clinically significant laboratory abnormalities have been noticed at week 8 visit, those laboratory evaluations will be repeated at the week 9 visit. A list of laboratory tests is included in [Table 4](#).

This document is confidential.

**Statistical Analysis Plan for Interventional Studies**

Sponsor: Teva Branded Pharmaceutical Products R&D, Inc./Nuvelution TS Pharma, INC.;  
 Protocol No.: TV50717-CNS-30060

Observed values (in SI units) and change from baseline to Week 8 will be summarized by treatment group. For hematology and chemistry panel, result will also be categorized as “Normal”, “Low”, or “High” based on their normal ranges. For urinalysis results, tests will be classified as “Normal” or “Abnormal”. Shift tables comparing laboratory test results from baseline to Week 8 will be presented.

All laboratory data will be listed. For hematology, chemistry, columns will be included for normal ranges and individual abnormal laboratory values will be flagged. Listing for urinalysis will include the microscopic examination provided for patients who have a positive result from the urinalysis dipstick evaluation.

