Note: Use of stimulant medications, including amphetamine, methylphenidate, and lisdexamfetamine, is allowed if primary use is for the treatment of ADHD, dosing has been stable for at least 2 weeks before screening, and no changes to dose or frequency are anticipated during the course of the study.

Note: Use of atomoxetine is allowed if the primary use is for the treatment of ADHD, dosing has been stable for at least 4 weeks before screening, and no changes to dose or frequency are anticipated during the course of the study.

Note: Use of benzodiazepines is allowed if primary use is not for tics and dosing has been stable for at least 4 weeks before screening.

Note: Use of topiramate (up to 200 mg/day) is allowed if dosing has been stable for at least 4 weeks before screening.

Note: Use of guanfacine or clonidine is allowed regardless of indication (ie, if prescribed for tics or TS) if the dosing has been stable for at least 4 weeks before screening and no changes to dose or frequency are anticipated during the course of the study. If discontinuation of either medication is anticipated due to ineffectiveness, poor tolerability, or patient/caregiver preference, discontinuation should occur 4 or more weeks prior to the screening visit.

- l. Patient has received treatment with deep brain stimulation, transcranial magnetic stimulation, or transcranial direct current stimulation within 4 weeks of the screening visit for reduction of tics.
- m. Patient has a QT interval corrected for heart rate using Fridericia's formula (QTcF) interval value >450 msec (males) or >460 msec (females), or >480 msec (with right bundle branch block) on a 12-lead electrocardiogram (ECG) at screening, or requires treatment with drugs known to prolong the QT interval (see Appendix H, [Table 10](#) for a complete list of prohibited QT-prolonging drugs).
- n. Patient has a history of torsades de pointes, congenital long QT syndrome, bradyarrhythmias, or uncompensated heart failure.
- o. Patient has evidence of hepatic impairment, as indicated by the following:
 - aspartate aminotransferase (AST) or alanine aminotransferase (ALT) $>2.5 \times$ the upper limit of the normal range (ULN) at screening
 - alkaline phosphatase (ALP) or total bilirubin $>2 \times$ ULN at screening

Note: Patients with Gilbert's syndrome are eligible to participate if approved by the medical monitor.

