7.1.5.1. Definition of a Serious Adverse Event

A serious adverse event is an adverse event occurring at any dose that results in any of the following outcomes or actions:

- results in death
- is life-threatening adverse event (ie, the patient was at risk of death at the time of the event); it does not refer to an event which hypothetically might have caused death if it were more severe
- requires inpatient hospitalization or prolongation of existing hospitalization, which means that hospital inpatient admission or prolongation of hospital stay were required for treatment of an adverse event, or that they occurred as a consequence of the event
Hospitalizations scheduled before the patient and caregiver/adult signed the informed consent/assent form will not be considered serious adverse events, unless there was worsening of the pre-existing condition during the patient's participation in this study
- results in persistent or significant disability/incapacity (refers to a substantial disruption of one's ability to conduct normal life functions)
- is a congenital anomaly/birth defect
- an important medical event that may not result in death, be life-threatening, or require hospitalization, but may jeopardize the patient and may require medical intervention to prevent one of the outcomes listed in this definition

Examples of such events are intensive treatment in an emergency room or at home for allergic bronchospasm; blood dyscrasias or convulsions that do not result in hospitalization; or the development of drug dependency or drug abuse. Note: Any suspected transmission of an infectious agent via a medicinal product is considered an important medical event

All occurrences of possible drug-induced liver injury that meet Hy's law criteria, defined as all of the below, must be reported by the investigator to the sponsor as a serious adverse event:

- alanine aminotransferase (ALT) or aspartate aminotransferase (AST) increase of >3x the upper limit of normal (ULN)
- total bilirubin increase of >2x ULN
- absence of initial findings of cholestasis (ie, no substantial increase of alkaline phosphatase [ALP])

An adverse event that does not meet any of the criteria for seriousness listed above will be regarded as a nonserious adverse event.

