**This document is confidential.**

## **6. General Aspects for Statistical Analysis**

### **6.1. General Methods**

Statistical methodology and analyses are in accordance with the principles outlined by the ICH E9 guidelines. All statistical analyses will be conducted using SAS statistical software version 9.3 or above.

Tables, listings and figures (TLFs) will be produced in accordance with the principles outlined by the ICH E3 guidelines. For most summary statistics, data will be analyzed by the following treatment groups: TEV-50717 High-Dose; TEV-50717 Low-Dose; Placebo. Total column will be included in all non-efficacy tables.

Data summaries will use descriptive statistics (number of patients [n], mean, standard deviation [SD], standard error [SE], median, minimum, and maximum) for continuous variables, and frequency and percentage of patients for categorical and ordinal variables, unless otherwise specified. For continuous variables, if  $n < 5$  then only median, min and max will be presented.

Unless otherwise specified, all statistical tests will be two-tailed using a 0.05 level of significance. All confidence intervals (CIs) will be two sided 95% CIs.

Only visits mapped to scheduled visits will be included in by-visit summaries. All visit assessment data will be included in shift tables and will appear in the patient listings.

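### SAP 9.5 shifts chemistry on Normal/Low/High only, so a large rise in a child already above range shows as no shift, and no legible table counts patients by arm against the protocol's Hy's law multiples of ULN

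*SAP*

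**What the plan says.** SAP 9.5 plans three kinds of laboratory output.

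- **Continuous summaries:** "Observed values (in SI units) and change from baseline to Week 8 will be summarized by treatment group". SAP 6.1 defines such summaries to include the minimum, median and maximum.
- **Categories and shifts:** "For hematology and chemistry panel, result will also be categorized as “Normal”, “Low”, or “High” based on their normal ranges", followed by "Shift tables comparing laboratory test results from baseline to Week 8 will be presented".
- **Listings:** all laboratory data are listed. For hematology and chemistry the listing carries the normal ranges, and "individual abnormal laboratory values will be flagged".

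Chemistry is scheduled at screening and at Week 8 or early termination (Protocol Table 2). SAP 9.5 adds a Week 9 repeat where a Week 8 abnormality is clinically significant. On shift tables in general, SAP 6.1 says "All visit assessment data will be included in shift tables".

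Protocol 4.2, criterion o, excludes ALT or AST only above 2.5x ULN, and ALP or total bilirubin only above 2x ULN, at screening. Protocol 7.1.5.1 requires a Hy's law case to be reported as a serious adverse event. It defines one by three conditions that must all hold: ALT or AST >3x ULN, total bilirubin >2x ULN, and no initial sign of cholestasis.

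**The concern.** Change in laboratory parameters is a named safety endpoint (Protocol 2.3, SAP 4.5). A shift table is where a reader looks for patients who moved in a harmful direction. Here the scale has one step above normal, and the entry criteria allow children to start on that step, so they cannot shift upward however far they rise. For a child who starts normal, a marginal rise and a very large one look the same.

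Elsewhere the SAP does count patients against limits. SAP 9.8 and its Table 5 define markedly abnormal vital signs. SAP 9.9 has QTcF thresholds and Table 6. SAP 9.14 shifts the C-SSRS to the worst category during treatment. The legible laboratory section has nothing similar, although the protocol already names multiples of ULN that matter. At stake is whether the study report can state, by arm, how many children crossed them.

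**Working it through.** The documents give no figure to reproduce on this point. The check applies the SAP 9.5 categories to values that the protocol allows.

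**Inputs**

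- Grading rule (SAP 9.5): a result is High if it is above the normal range, taken here as >1x ULN.
- Permitted baseline (Protocol 4.2, criterion o): ALT or AST up to 2.5x ULN; bilirubin up to 2x ULN.
- Baseline (SAP 6.2.1): the last non-missing value on or before first dose. For chemistry this is normally the screening sample, because none is scheduled on Day 1.
- Multiples used in the Hy's law definition (Protocol 7.1.5.1): 3x ULN for ALT or AST, 2x ULN for bilirubin.

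**Step 1: map ALT through the categories.**

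| Baseline ALT (x ULN) | Week 8 ALT (x ULN) | Tabulated as |
|---|---|---|
| 1.2, 2.0 or 2.5 | 3.1, 5 or 10 | High to High, no shift (all 9 combinations) |
| 2.0 | 1.1 | High to High, no shift |
| 0.8 | 1.1 | Normal to High |
| 0.8 | 3.1, 5 or 10 | Normal to High |

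A fall from 2.0 to 1.1x ULN and a rise from 2.0 to 10x ULN land in the same cell. The 3x ULN level is invisible from either starting category. Bilirubin behaves the same way: 1.5x to 2.1x ULN is High to High.

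**Step 2: see what the arm mean shows.** In an arm of 50, one child's rise moves the mean change by (Week 8 value − baseline) / 50:

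- 2.0 to 3.5x ULN: 1.5 / 50 = 0.03x ULN
- 2.4 to 3.1x ULN: 0.7 / 50 = 0.014x ULN
- 2.5 to 10x ULN: 7.5 / 50 = 0.15x ULN

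**Step 3: see what the maximum shows.** It reveals the single most extreme value in an arm, in SI units, but not how many children crossed a level. ALT and bilirubin are summarized separately, so it cannot show whether both were raised in the same child.

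**Step 4: look for a count elsewhere in the readable text.** SAP 9.4 tabulates events by system organ class and preferred term. Its SMQ summaries cover suicide/self-injury, depression and Parkinson-like events, and none is hepatic. Protocol 9.7.1 asks only for descriptive laboratory summaries. No by-arm count against a multiple of ULN was found. The SAP's table index is blacked out, so its titles could not be checked.

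**Step 5: timing.** SAP 9.5 describes the shift as baseline to Week 8, while SAP 6.1 admits all visit data to shift tables. The visible rules in SAP 6.4 prefer a scheduled visit to an early termination or unscheduled one in the same window. The text does not say that the worst post-baseline value is used.

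**The case against.** The strongest reply is that one table is coarse but the information is not lost. Much of that stands.

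- **A reader might infer that the protocol sets 3x ULN as a limit on its own.** It does not. Protocol 7.1.5.1 uses it only jointly with bilirubin and absence of cholestasis.
- **A reader might infer that serious rises never reach a comparison by arm.** That goes too far. A full Hy's law case is a serious adverse event, and under Protocol 7.5 a laboratory result judged clinically significant is recorded as an adverse event. Both enter the by-arm tables of SAP 9.4. A child at 10x ULN could also appear as the arm's maximum, and every value is listed with its normal range. What remains is that the event tables depend on judgement and preferred term, and an ALT above 3x ULN with normal bilirubin is not counted against that multiple anywhere legible.
- **The SAP follows the protocol.** Protocol 9.7.1 prespecifies QTcF cut-offs but no liver ones, and Protocol 7.1.6 names no adverse events of special interest. This is therefore a gap in presentation, not a contradiction.
- **Early termination and unscheduled samples are partly handled already** by SAP 6.1 and 6.4. That is true, though still on three levels and without a worst-value rule.
- **A reader might also want cut-offs for creatinine at 1.5x ULN and ALP at 2x ULN.** Those figures are entry criteria in Protocol 4.2, not post-baseline safety limits. For ALP, the Hy's law text speaks only of a substantial increase, without a number.
- **Zero-event confidence bounds would not measure this gap.** They describe what a sample of a given size can exclude, and a zero count could be read from the planned listing.

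**Conclusion.** The point holds as a modest, inexpensive improvement to the laboratory tables. Under the legible SAP 9.5, every rise past 3x ULN from a baseline above range is shown as no shift (9 of 9 combinations tried), and rises from normal are not graded by size. No readable table gives, by arm, the number of patients above the multiples of ULN in the protocol's Hy's law definition, singly or together. The other outputs show such rises in part, and none supplies that count.

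The conclusion assumes that High means above 1x ULN and that the redacted table index contains no such table. The number of children who will enter above range, or cross these levels, cannot be obtained from the documents. Entry requires good general health, and medical monitor approval where two or more liver tests are abnormal, so it may be small. The primary and secondary efficacy conclusions are not affected.

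**What to change.** In SAP 9.5, for the safety analysis set and by arm:

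1. Add the number and percentage of patients with any post-baseline ALT or AST >3x ULN, any total bilirubin >2x ULN, and both together. Label the last row as potential Hy's law, show ALP beside it, and have the sponsor define what counts as a substantial ALP increase. State whether both values must come from the same sample.
2. For ALT, AST and bilirubin, show the shift from baseline to worst post-baseline value in ULN bands: at or below 1; above 1 up to the multiple (3 for ALT and AST, 2 for bilirubin); above the multiple. With these bands all nine ALT combinations in the working move up one band. The three-level shift can stay for the other analytes.
3. State that both tables use all post-baseline samples, including early termination and unscheduled ones, in line with SAP 6.1, and say how Week 9 repeats are treated.

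Creatinine and ALP cut-offs need not be added. The cost is SAP wording and one or two extra descriptive tables, with no new samples and no change to conduct. If the redacted index already lists such tables, a sentence in SAP 9.5 defining them is enough.

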**Table 4: List of Laboratory Tests**

Serum Chemistry	Hematology	Urinalysis
calcium	hemoglobin	protein
phosphate	hematocrit	glucose
sodium	red blood cell (RBC)	ketones
potassium	count mean cell volume	blood (hemoglobin)
chloride	platelet count	pH
creatinine	white blood cell (WBC) count, and	specific gravity
glucose	differential count	microscopic
magnesium	- absolute neutrophil count	- bacteria
blood urea nitrogen (BUN)	(ANC)	- RBCs
total cholesterol	- polymorphonuclear	- WBCs
uric acid	leukocytes (neutrophils)	- casts
alanine aminotransferase (ALT)	- lymphocytes	- crystals
aspartate aminotransferase (AST)	- eosinophils	
lactate dehydrogenase (LDH)	- monocytes	
alkaline phosphatase (ALP)	- basophils	
bicarbonate or carbon dioxide		
total protein		
albumin		
total bilirubin		
direct bilirubin		

### 9.6. Pregnancy

Pregnancy tests will be performed for females who are postmenarchal or  $\geq 12$  years of age. Urine test will be administered at baseline, and serum test will be administered at screening and Week 8. The pregnancy data will be presented in a data listing.

### 9.7. Urine Drug Screening

Urine drug screening tests are collected at screening and week 8. The urine drug screening data will be presented in a data listing.

This document is confidential.

## **9.8. Vital Signs**

Vital signs will be measured at screening, baseline, and weeks 2, 4, 8, and 9. Measurements of vital signs will include measurement of pulse, blood pressure (BP), weight, body temperature, and respiratory rate. Pulse and BP in supine or semi-erect/seated position will be measured in each scheduled or unscheduled visits. In addition, standing BP and pulse will be taken at baseline, weeks 4, and 8. BMI will be computed similarly as in Section 7.2 at Week 8 and early termination visits. Weight and height at the visit will be used. Normal age and sex-based z-scores, percentiles for BMI, and BMI categories will also be determined using the WHO growth charts similarly as in Section 7.2.

Orthostatic systolic and diastolic BP and pulse will be calculated as supine or semi-erect/seated measurement – standing measurement. Orthostatic hypotension (determined by blood pressure measurements only) is defined as having either a  $\geq 20$  mmHg reduction from supine to standing position in systolic blood pressure (SBP) or  $\geq 10$  mmHg reduction from supine to standing position in diastolic blood pressure (DBP) or both. Orthostatic tachycardia is defined as pulse increase  $\geq 20$  bpm from supine to standing position.

Observed values, change from baseline, for each vital sign parameter and position will be summarized at each visit by treatment and overall.

In addition, orthostatic hypotension or orthostatic tachycardia occurrences, and the markedly abnormal post-baseline vital signs results will also be summarized for patients with at least one markedly abnormal value during the treatment period according to criteria specified in Table 5. A listing will be provided for all markedly abnormal vital signs. A shift table for BMI age and sex adjusted categories will be presented comparing shifts from the baseline visit to week 8. Percentages will be based on the number of safety patients with a non-missing value for both the baseline and post-baseline visit for the given vital sign.

This document is confidential.

**Table 5: Criteria for Markedly Abnormal Vital Sign Parameters by Age**

Parameter (unit)	Age (years old)	Markedly Low	Markedly High
SBP (supine, standing) (mmHg)	6-12	Value $\leq$ 70 and $\geq$ 20 decrease from baseline	Value $\geq$ 120 and $\geq$ 20 increase from baseline
	13-18	Value $\leq$ 90 and $\geq$ 20 decrease from baseline	Value $\geq$ 135 and $\geq$ 20 increase from baseline
DBP (supine, standing) (mmHg)	6-12	Value $\leq$ 40 and $\geq$ 15 decrease from baseline	Value $\geq$ 80 and $\geq$ 15 increase from baseline
	13-18	Value $\leq$ 50 and $\geq$ 15 decrease from baseline	Value $\geq$ 90 and $\geq$ 15 increase from baseline
Pulse rate (supine, standing) (bpm)	6-10	Value $\leq$ 60 and $\geq$ 15 decrease from baseline	Value $\geq$ 135 and $\geq$ 15 increase from baseline
	11-18	Value $\leq$ 50 and $\geq$ 15 decrease from baseline	Value $\geq$ 120 and $\geq$ 15 increase from baseline
SBP orthostatic criteria (mmHg)	~	$\geq$ 20 decrease from supine to standing position	NA
DBP orthostatic criteria (mmHg)	~	$\geq$ 10 decrease from supine to standing position	NA
Pulse rate orthostatic criteria (bpm)	~	NA	$\geq$ 20 increase from supine to standing position
Temperature ( $^{\circ}$ C)	~	NA	Value $\geq$ 38.3 $^{\circ}$ C and $\geq$ 0.8 $^{\circ}$ C increase from baseline

Note: ~ means that the abnormal range is applicable for all patients within age group: 6 to 17 years old.

Vital signs data will be provided in a data listing.

### 9.9. ECG

Assessment of Standard 12-lead ECG are obtained at screening, baseline, weeks 4 and 8. A central ECG Standard 12-lead ECG will record heart rate (HR), PR interval, RR interval, QT interval, Frederica's corrected QT interval (QTcF), and QRS duration. The overall ECG assessment will be centrally reported as "Normal" or "Abnormal" with respect to relevant abnormalities. If a post-baseline QTcF value  $>$ 500 msec or change from baseline  $>$ 60 msec is found, the investigator should repeat the ECG assessment twice. In this case, the confirmed QTcF, defined as the average of all 3 ECG values at the visit, will be used for summary. If ECG tests are repeated on the same day for any other reason per investigators discretion, the average of all ECG values on that day will be used for summary.

This document is confidential.

**Statistical Analysis Plan for Interventional Studies**

Sponsor: Teva Branded Pharmaceutical Products R&D, Inc./Nuvelution TS Pharma, INC.;  
Protocol No.: TV50717-CNS-30060

---

Observed results of each ECG parameter and change from baseline will be summarized by treatment and overall, and by visit using descriptive statistics.

In addition, for QTcF, average baseline confirmed QTcF (the average of the screening and Day 1 QTcF), and the change from average baseline will be summarized by treatment and overall, and by visit using descriptive statistics.

QTcF values will be classified as having QTc prolongation according to the following conditions.

QTc Prolongation
Confirmed QTcF >450 msec
Confirmed QTcF >480 msec
Confirmed QTcF >500 msec
Increase from baseline QTcF $\geq$ 60 msec
Increase from average baseline confirmed QTcF $\geq$ 60 msec
Increase from baseline QTcF $\geq$ 30 msec
Increase from average baseline confirmed QTcF $\geq$ 30 msec

The number and percentage of patients with QTc prolongation will be summarized by treatment and overall, and by visit.

A shift table comparing the overall ECG assessment from baseline to each visit will be presented.

In addition, the abnormal post-baseline ECG results will also be summarized for patients with at least one abnormal value during the treatment period. The summary will be completed by treatment and overall, and age groups (6 - < 8 years, 8 - < 12 years, and 12 - < 16 years), and overall using the age at the time of the individual assessment.

Criteria for abnormal values used in the study are presented in [Table 6](#).

This document is confidential.

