Safety Analyses: All adverse events will be coded using the Medical Dictionary for Regulatory Activities. Each patient will be counted only once in each preferred term or system organ class category for the analyses of safety. Summaries will be presented for all adverse events, adverse events determined by the investigator to be related to study treatment, serious adverse events, and adverse events causing withdrawal from the study. Summaries will be presented by treatment group and for all patients. Patient listings of serious adverse events and adverse events leading to withdrawal will be presented.

Observed values and changes from baseline in laboratory results and vital signs will be summarized descriptively.

Observed values in ECG parameters will be summarized, and counts and percentages of abnormal findings will be presented. In addition, the number and percentage of patients with on-treatment QTcF values > 450 , > 480 , or > 500 msec and change from baseline > 30 or > 60 msec will be presented.

The use of concomitant medications will be summarized by therapeutic class using descriptive statistics. Concomitant medications will include all medications taken while the patient is treated with IMP.

Observed values in the C-SSRS and observed values and changes from baseline in the CDI-2 (Parent and Self-report Profiles) will be presented by treatment group for all patients.

Sensitivity Analysis: Sensitivity analyses of primary and key secondary endpoints will be conducted using the per-protocol analysis set. Sensitivity analyses for missing data and the statistical model will be provided in the statistical analysis plan.

TABLE OF CONTENTS

TITLE PAGE	1
AMENDMENT HISTORY	2
INVESTIGATOR AGREEMENT.....	3
SPONSOR PROTOCOL APPROVAL	4
COORDINATING INVESTIGATOR AGREEMENT	5
COORDINATING INVESTIGATOR AGREEMENT	6
CLINICAL LABORATORIES AND OTHER DEPARTMENTS AND INSTITUTIONS	7
CLINICAL STUDY PROTOCOL SYNOPSIS.....	10
LIST OF ABBREVIATIONS.....	31
1. INTRODUCTION AND BACKGROUND INFORMATION	35
1.1. Introduction.....	35
1.2. Name and Description of Investigational Product.....	36
1.3. Findings from Nonclinical and Clinical Studies.....	36
1.3.1. Nonclinical Studies.....	36
1.3.1.1. Nonclinical Pharmacology.....	36
1.3.1.2. Nonclinical Pharmacokinetics and Drug Metabolism	37
1.3.1.3. Toxicology	37
1.3.2. Clinical Studies.....	38
1.3.2.1. Clinical Pharmacology Studies.....	38
1.3.2.2. Clinical Safety and Efficacy Studies	39

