9.7.1. Safety Analysis

All adverse events will be coded using the Medical Dictionary for Regulatory Activities. Each patient will be counted only once in each preferred term or system organ class category for the analyses of safety. Summaries will be presented for all adverse events, adverse events determined by the investigator to be related to study treatment, serious adverse events, and adverse events causing withdrawal from the study. Summaries will be presented by treatment group and for all patients. Patient listings of serious adverse events and adverse events leading to withdrawal will be presented.

Observed values and changes from baseline in laboratory results and vital signs will be summarized descriptively.

Observed values in ECG parameters will be summarized, and counts and percentages of abnormal findings will be presented. In addition, the number and percentage of patients with

on-treatment QTcF values >450, >480, or >500 msec and change from baseline >30 or >60 msec, will be presented.

The use of concomitant medications will be summarized by therapeutic class using descriptive statistics. Concomitant medications will include all medications taken while the patient is treated with IMP.

Observed values in the C-SSRS and observed values and changes from baseline in the CDI-2 (Parent and Self-report Profiles) will be presented by treatment group for all patients.

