### 6.4. Visit Windows

[Redacted text block]

[Redacted text block]

[Redacted]	[Redacted]	[Redacted]	[Redacted]
[Redacted]	[Redacted]	[Redacted]	[Redacted]
[Redacted]	[Redacted]	[Redacted]	[Redacted]
[Redacted]	[Redacted]	[Redacted]	[Redacted]
[Redacted]	[Redacted]	[Redacted]	[Redacted]
[Redacted]	[Redacted]	[Redacted]	[Redacted]
[Redacted]	[Redacted]	[Redacted]	[Redacted]
[Redacted]	[Redacted]	[Redacted]	[Redacted]
[Redacted]	[Redacted]	[Redacted]	[Redacted]
[Redacted]	[Redacted]	[Redacted]	[Redacted]

[Redacted text block]

[Redacted]	[Redacted]	[Redacted]	[Redacted]
[Redacted]	[Redacted]	[Redacted]	[Redacted]
[Redacted]	[Redacted]	[Redacted]	[Redacted]
[Redacted]	[Redacted]	[Redacted]	[Redacted]
[Redacted]	[Redacted]	[Redacted]	[Redacted]
[Redacted]	[Redacted]	[Redacted]	[Redacted]
[Redacted]	[Redacted]	[Redacted]	[Redacted]
[Redacted]	[Redacted]	[Redacted]	[Redacted]
[Redacted]	[Redacted]	[Redacted]	[Redacted]
[Redacted]	[Redacted]	[Redacted]	[Redacted]

After mapping the data to the analysis visits of unscheduled and early termination visits, the following rules will apply unless other handling is specified for a particular analysis.

- If there is scheduled visit in the analysis window, scheduled visit will be selected.
- If there is no scheduled visit, but early termination visit, early termination visit will be selected.
- If there are no scheduled or early termination visits, the unscheduled visit will be selected. If there are multiple unscheduled visits, the following rules will be used in sequential order:
  - The record closest to the planned assessment day will be selected for analysis.

This document is confidential.

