## **9. Safety**

The safety endpoints for this study are as follows:

- Incidence of adverse events
- Observed values and changes from baseline in vital signs
- Observed values and change from baseline in the Children's Depression Inventory, Second Edition (CDI-2), Parent and Self-report Profiles
- Observed values in the Children's Columbia-Suicide Severity Rating Scale (C-SSRS)
- Observed values in electrocardiogram (ECG) parameters and shifts from screening for clinically significant abnormal findings
- Observed values and changes from screening in clinical laboratory parameters (hematology, chemistry, and urinalysis)

The safety analysis set will be used for all safety analyses. Summaries will be presented by treatment group and for all patients.

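### The readable text of SAP 9.9 counts QTc prolongation only visit by visit, which cannot give the per-patient on-treatment count that the protocol calls for

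*SAP*

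**What the plan says.** Protocol 9.7.1, repeated in the synopsis, promises "the number and percentage of patients with on-treatment QTcF values" beyond set limits. The limits are "on-treatment QTcF values >450, >480, or >500 msec and change from baseline >30 or >60 msec". The unit is the patient, the period is on treatment, and no visit is mentioned.

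SAP 9.9 lists seven QTc categories: three absolute limits on confirmed QTcF, and increases of 30 and 60 msec against each of two baselines. It then states: "The number and percentage of patients with QTc prolongation will be summarized by treatment and overall, and by visit".

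Two general rules decide which ECGs reach that table. SAP 6.1: "Only visits mapped to scheduled visits will be included in by-visit summaries". SAP 6.4: "If there is scheduled visit in the analysis window, scheduled visit will be selected". An early termination record is used only if the window has no scheduled one, and an unscheduled record only if it has neither. SAP 6.4 allows a particular analysis to specify other handling. SAP 9.9 specifies only that repeat ECGs are averaged.

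SAP 9.9 also has a table of patients with one or more abnormal ECG values in the treatment period. Its criteria are in Table 6, which lists heart rate, PR interval and QRS interval.

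**The concern.** QTcF has an exclusion limit (Protocol 4.2) and a level at which study drug must be stopped once the value is confirmed (Protocol 4.3, 7.1.7 and 7.8). A reader of the safety results will want to know what share of each arm was ever prolonged on drug. That is the natural reading of the protocol's count.

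The SAP gives comparable any-time or worst-value summaries elsewhere: markedly abnormal vital signs in 9.8 and the worst C-SSRS category in 9.14. For QTcF the readable text gives only separate visit rows. There are two possible losses. Patients prolonged at different visits are never combined into one count, and an ECG taken between visits because of a safety concern can be displaced by the routine one in the same window. Both push the displayed percentages below the share ever prolonged, never above it.

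**Working it through.** The plan states no QTc rate, so there is no figure to reproduce. The check compares texts and then uses arithmetic for illustration.

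**1. Does *overall* in SAP 9.9 mean any time?** No. The same phrase governs the continuous ECG summaries: "Observed results of each ECG parameter and change from baseline will be summarized by treatment and overall, and by visit using descriptive statistics". A mean pooled over time is not intended there. SAP 9 also says: "Summaries will be presented by treatment group and for all patients". *Overall* is the all-patients column.

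**2. Does another readable table supply the count?** No.
- The any-time abnormal-value table uses Table 6, without QTcF.
- The ECG shift table concerns the central Normal/Abnormal assessment, not the QTcF limits.
- SAP 12, where readable, names only a new exploratory endpoint as a change from the protocol.

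**3. What can two visit rows say?** The scheduled on-treatment ECGs are at weeks 4 and 8 (SAP 9.9). Let p be the share meeting a limit at each visit. The share meeting it at either visit is p if the same patients are affected, 1 − (1 − p)² if the visits are independent, and 2p if different patients are affected. The values of p are assumed.

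| p at each visit | same patients | independent | different patients | patients per 50 |
|---|---|---|---|---|
| 2% | 2% | 3.96% | 4% | 1 to 2 |
| 5% | 5% | 9.75% | 10% | 2.5 to 5 |
| 10% | 10% | 19% | 20% | 5 to 10 |

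The smallest case: in an arm of 50, one patient is above 450 msec only at week 4 and another only at week 8. The table shows 1/50 = 2% twice. The patient-level figure is 2/50 = 4%.

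**4. What can unscheduled ECGs add?** Protocol Table 2 permits them at the investigator's discretion. Suppose a share u of patients has one extra on-treatment ECG, positive with probability q. With independence, the any-time share is 1 − (1 − p)²(1 − uq). For p = 5%, u = 10% and q = 30%, this is 1 − 0.9025 × 0.97 = 12.5%. Over u from 5% to 20% and q from 10% to 30%, it runs from 10.2% to 15.2%. All of these inputs are assumptions.

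**5. How would an ECG be displaced?** Assume the week 4 analysis window reaches at least the protocol's visit tolerance of ±3 days (the SAP's own windows are redacted). A patient has a scheduled ECG of 430 msec on day 28 and an unscheduled one on day 31 whose confirmed average is 505 msec, and the drug is stopped. Under SAP 6.4 the week 4 row uses 430 msec, and the 505 msec enters no QTc row.

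A separate difference, not counted here: the protocol sets increases at above 30 and 60 msec, the SAP at 30 and 60 msec or more.

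**The case against.** The strongest reply is that the omission cannot be proved. The index of tables and the opening of SAP 6.4 are redacted, and an any-time row or an ECG-specific rule could sit there. This stands. A reader might infer that the protocol's count will not be produced; the documents show only that the readable text does not specify it.

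Second, the protocol does not say any time or maximum, and counts at weeks 4 and 8 are themselves on-treatment counts. This is a fair point of wording. But a number of patients with on-treatment values, given without visits, is most naturally one count per patient.

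Third, a reader might infer that a value that stopped a patient's drug could vanish from the report. It would not. SAP 6.1 keeps all visit data in the listings. Under Protocol 7.8 a clinically significant ECG finding is an adverse event, and SAP 9.4 tabulates events leading to discontinuation or interruption. The gap is in one summary count.

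Fourth, it would be too strong to say that unscheduled ECGs are dropped in general. They are used when the window has no scheduled or early termination record, and same-day repeats are averaged in. A single high reading that its repeats do not confirm is left out of the absolute rows by design.

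Finally, the display is descriptive, affects no hypothesis test, and with about 150 patients could be rebuilt from the listings. That limits the weight of the point. It does not remove the mismatch with the protocol, and a reader should not have to derive a planned safety figure by hand.

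**Conclusion.** The point holds in a limited form. The loss across visits needs no assumption about windows: with two scheduled ECGs, the share ever prolonged can be up to twice the share at each visit when the visit shares are equal, and the by-visit rows cannot show where in that range it lies. The loss within a window is real under the readable selection rules, but it is confined to ECGs on another day in a window that already holds a scheduled record. Its frequency is unknown, because the documents give neither QTc rates nor the number of unscheduled ECGs.

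The conclusion rests on reading the protocol's count as once per patient over the treatment period, and on the redacted material containing no such row. If the sponsor already plans one, a sentence in SAP 9.9 settles the matter. No efficacy conclusion, data collection or stopping rule is affected.

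**What to change.** In SAP 9.9, add a block to the QTc table for any time during the treatment period:

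- Count each patient once per threshold, on the highest post-baseline QTcF and the largest increase, the increase against each baseline that SAP 9.9 already uses.
- Use the SAP's confirmed or averaged value where an ECG was repeated.
- Include every scheduled, unscheduled and early termination ECG after the first dose through the week 8 or early termination visit. A cut-off at the last dose would not do, because the early termination visit follows the last dose and its ECG could be lost.
- State that the one-record-per-window rule in SAP 6.4 does not apply to this block.
- Keep the by-visit table as support.

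The cost is some SAP wording and one table block on data already collected. The reported prolongation rate may be slightly less favourable than the by-visit rows suggest.
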